8. STUDY INTERVENTION

8.1 Identity of Investigational Products (treatment / medical device)

The dosage of Amara is 3 x 10-20 drops per day prior to meals.

8.1.1 Experimental Intervention (treatment / medical device)

The bitter substances Artemisia absinthium, Cichorium intybus, Juniperus and Gentiana lutea, Amara Drops contain also Centaurium, Peucedanum, Achillea millefolia, Salvia officinalis and Taraxacum are held in an alcohol-based tincture. Amara is an herbal preparation manufactured by Weleda AG (Switzerland), according to Good Manufacturing Practice.

8.1.2 Control Intervention (standard/routine/comparator treatment / medical device)

No control intervention.

8.1.3 Packaging, Labelling and Supply (re-supply)

The Amara drops to be used in this study are a standard commercial product. They will be available in the standard labelled, brown glass. One glass bottle contains 50ml (enough for minimum 100 doses à

20 drops). The manufacturer Weleda AG will supply us with the medication in batches. The pharmacy at Clinic Arlesheim will print instructions on the dose and when to take the medication on an additional label.

8.1.4 Storage Conditions

The recommended storage temperature 15-25° C will be complied with. The Amara bottles to be used in the study will be stored in a lockable medicine cabinet at the out-patient clinic in an air-conditioned room at constant temperature. 60 glass bottles can be stored at once.

8.2 Administration of experimental and control interventions

8.2.1 Experimental Intervention

See chapter 8.1.1.

8.2.2 Control Intervention

No control intervention.

8.3 Dose modifications

Participants can vary the dose of the prescribed drug dose within set limits (10-20 drops with meals). This should not be exceeded even in case of worsening symptoms.

8.4 Compliance with study intervention

Compliance will be assessed by a smart phone app (patients will be asked to confirm intake every day). At the end of the study, the bottles will be weighed to determine the actual dose taken during study procedures. Before analysing the data, we will determine the target-actual-difference of the Amara drops taken for each participant. Less than 50 % of prescribed intake is considered as insufficient compliance. In case of insufficient compliance of participants, those data have to be excluded from the per protocol analysis.

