	Amara Drops will be dispensed with 10-20 drops (0.25-0.50ml) taken three times a day prior to meals for 4 weeks. Patients are free to vary the dose between these limits as considered appropriate. The amount taken will be monitored by checking the volume remaining in the bottle at the end of the 4-week intervention. During this time, patients will continue reporting the presence and severity of dyspeptic symptoms and any side effects into the app.
	At the end of the study period (Study Visit #3) the questionnaires including LCT and the ¹³ C-breath test measurement with concurrent high-resolution electro-gastrography (Gastric Alimetry System) and heart rate monitoring plus concurrent assessment of visceral sensitivity will be repeated. Additionally, the patients will be asked if their global satisfaction was better on Amara treatment, whether they wish to continue treatment and /or recommend the treatment to others with similar symptoms. Questionnaires and diary entries on side effects are also available as paper version.
Risk / Benefit Assessment	The initial assessment of patients with functional dyspepsia will adhere to international guidelines on the investigation of this condition. Amara Drops (Weleda) is a proprietary preparation that has been marketed over the counter (OTC) for many years. No serious side effects have been reported. ¹³ C-breath test gastric emptying studies and other measurements of gastric function (e.g. electro-gastrography) are indicated in patients with functional dyspepsia that do not respond to first-line, dietary management, and empirical treatment. These tests are non-invasive and not radioactive and is associated with no adverse outcomes. Clinical validation studies report that the intake of the 400ml (300kcal) Nottingham Test Meal is tolerated by all healthy controls and >95% of patients with functional dyspepsia without inducing vomiting.
Objectives:	The aim of the present study is to find out if the regular intake of Amara has effects on the perceived symptom burden reported by patients with functional dyspepsia. Since dyspeptic symptoms may be associated with abnormal gastric motor and sensory function, these aspects will be assessed by validated methods.

Outcomes:	 Primary objective / outcome measure: change in perceived symptom burden during regular intake of Amara assessed by the Leuven Dyspepsia Score between visit 1 (off treatment) and 3 (on treatment).

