3.5 Dose Rationale

Patients will take 3 x 10-20 drops of Amara before meals daily for four weeks (see section 8.1). The standard dose of this preparation is 10-15 drops before meals to "stimulate the digestive process"; however, patients are encouraged to adapt the dose to their requirements. Patient compliance will be assessed using a smart phone application that will record whether medication was taken and the severity of symptoms at the end of each day. Patient compliance (i.e. actual intake) will be checked by weighing the bottle at the end of the treatment period.

A 2-4-week run-in period between screening and the start of treatment is applied to ensure that the severity of symptoms is representative (patients tend to present during periods with relatively severe symptoms, thus run-in periods reduce the influence of spontaneous "regression to the mean" providing false positive results). The treatment period of 4-weeks is in accordance with the above-mentioned studies for other aromatic bitter substances and represents the minimum recommendation for study duration in functional gastrointestinal disorders.(15)

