An appointment will be made 2-4-weeks later for the second study visit at which time the ¹³C gastric emptying study will be performed again. The run-in period is 2-4-weeks. This reduces the influence of spontaneous "regression to the mean" (i.e., false positive results).(15)

Gastric motor and sensory function will be assessed by ingestion of the 400ml, 300kcal Nottingham Test Meal (NTM) labelled with ¹³C acetate. This provides both an assessment of patient symptoms / visceral sensitivity to gastric filling with the 400ml liquid nutrient meal and also an assessment of gastric emptying. The 400ml NTM can be ingested by >95% of patients with functional dyspepsia.(19,

24) The ¹³C isotope is not radioactive, it takes 2-hours to complete and this technique is very appropriate for repeated assessment of gastric emptying.(16) In a subset of 20 consecutive patients, gastric electrical activity will be measured before, during and after ingestion of the Nottingham Test Meal using the non-invasive Gastric Alimetry System (high-resolution gastric mapping / electro-gastrography). Concurrent heart rate monitoring will provide an assessment of cardiovagal tone / autonomic nervous function.

The treatment period with Amara drops is four weeks per patient; participants will be instructed to take 10-20 drops of the herbal medicine Amara three times a day before meals over 28 days. This treatment period is in accordance with previous studies for aromatic bitter substances and represents the minimum recommendation for study duration in functional gastrointestinal disorders.(15) During the treatment period patients will record their symptoms using a mobile application (reminder will be sent at 21:00 every day). In addition, patients can note side effects that they perceive to be caused by Amara. If participants do not regularly provide this information, then a team member will call to ask if they have any problems.

At the end of the treatment period the participant will return to Clinic Arlesheim for repeat assessment. The LDQ and other patient related outcomes will be assessed again and ¹³C gastric emptying study will be repeated on treatment.

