11.4.3 Secondary Analyses

In the per protocol analysis (after four weeks), only patients who have taken at least half of the study medication will be included. Comparisons will be made between scores at study begin and scores after four weeks of treatment. Following covariates will be included in multivariate models: age, gender, dyspepsia symptom severity (LDQ), other gastrointestinal symptoms, psychological state and gastric function (sensitivity, emptying) at baseline.

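### The per-protocol compliance cut-off compares bottle weight with a dose the patient chooses, so it can fall anywhere from 10.5 to 21 ml and mixes chosen dose with missed doses

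*Protocol*

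**What the plan says.** Section 8.4 names two sources of compliance data. One is the smartphone app, in which "patients will be asked to confirm intake every day". The other is the returned bottle: "the bottles will be weighed to determine the actual dose taken during study procedures". Before analysis, a difference between target and actual drops is to be worked out for each participant. The rule is then: "Less than 50 % of prescribed intake is considered as insufficient compliance", and such patients leave the per-protocol analysis. Section 11.4.3 states the inclusion side: "only patients who have taken at least half of the study medication will be included".

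The dose is a range. Section 6.1 prescribes "10-20 drops of the herbal medicine Amara three times a day before meals over 28 days". The Study Synopsis (Protocol Summary) gives the range as 0.25 to 0.50 ml and adds: "Patients are free to vary the dose between these limits as considered appropriate". Section 8.3 repeats this: "Participants can vary the dose of the prescribed drug dose within set limits". Section 3.5 gives 10 to 15 drops as the standard dose, encourages patients to adapt it, and describes the app as "a smart phone application that will record whether medication was taken".

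Compliance is used a second time. Section 4.3, factor (viii), lists it among the factors that may predict outcome, and section 9.3.2 says it is assessed by weighing the bottles.

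**The concern.** A percentage of prescribed intake needs a denominator, and the prescription has a two-fold range. Any dose from 10 to 20 drops is within instructions, so low total use can mean a permitted low dose taken faithfully or a higher dose often skipped. Bottle weight gives only the total.

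Membership of the per-protocol set would therefore depend on the dose a patient prefers as well as on adherence. The same ambiguity enters the predictor analysis: 21 ml used may be all 84 doses at 10 drops or 42 doses at 20 drops.

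Choosing a number later in an analysis plan does not remove this. For any single volume, a 10-drop patient needs twice as many doses as a 20-drop patient. A target for each individual would need a record of the dose each patient took, and the protocol describes no such record.

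**Working it through.** **Inputs**
- Volume per dose: 10 drops = 0.25 ml, 20 drops = 0.50 ml (Study Synopsis and section 3.1), hence 15 drops = 0.375 ml.
- Schedule: 3 doses a day for 28 days (section 6.1), so 3 × 28 = 84 doses.
- Cut-off: 50% (section 8.4).

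**Check against the protocol's own figure.** Section 8.1.3 says a 50 ml bottle holds at least 100 doses of 20 drops. 50 / 0.50 = 100, so the drop-to-volume conversion is consistent.

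**Cut-off by assumed target.** Full intake = 84 × ml per dose; cut-off = 0.5 × full intake.
- 10 drops: 84 × 0.25 = 21 ml; cut-off 10.5 ml.
- 15 drops: 84 × 0.375 = 31.5 ml; cut-off 15.75 ml.
- 20 drops: 84 × 0.50 = 42 ml; cut-off 21 ml.

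**Doses needed to pass.** Doses = cut-off / ml per dose, as a share of 84.

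| Cut-off | Patient on 10 drops | Patient on 15 drops | Patient on 20 drops |
|---|---|---|---|
| 10.5 ml | 42 (50%) | 28 (33%) | 21 (25%) |
| 15.75 ml | 63 (75%) | 42 (50%) | 31.5, so 32 (38%) |
| 21 ml | 84 (100%) | 56 (67%) | 42 (50%) |

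Only the diagonal gives the intended 50%. For any cut-off V, the ratio of doses needed is (V / 0.25) / (V / 0.50) = 2.

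**The two ends**
- At 21 ml, a 10-drop patient who misses one dose has used 83 × 0.25 = 20.75 ml. 20.75 / 42 = 49.4%, so the patient is excluded. With no dose missed, use is exactly 21 ml and the patient is kept.
- At 10.5 ml, a 20-drop patient passes with 21 × 0.50 = 10.5 ml, having skipped 84 − 21 = 63 doses.

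**What the app adds, as described.** One confirmed day could stand for anything from 1 × 0.25 = 0.25 ml to 3 × 0.50 = 1.50 ml, a 6-fold range.

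**What bottle weight can settle alone.** If every dose lies between 0.25 and 0.50 ml, the number of doses N satisfies V / 0.50 ≤ N ≤ V / 0.25.
- V below 10.5 ml: N is below 10.5 / 0.25 = 42, so fewer than half of 84.
- V of at least 21 ml: N is at least 21 / 0.50 = 42, so at least half.
- In between, weight does not decide. For example, 14 ml is 14 / 0.25 = 56 doses (67%) at 10 drops or 14 / 0.50 = 28 doses (33%) at 20 drops.

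**The case against.** The strongest reply is that section 8.4 already fixes the threshold, the measure, the timing and the consequence, and leaves only an operational target, which an analysis plan could supply. Because the comparison is made for each participant, the target could be individual. This stands in part: the protocol does not say that one common volume will be used. But an individual target needs the chosen dose, and the app is described only as confirming intake. The app's fields are not shown; if they already record doses and drops, the data gap closes and only the wording remains.

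It can also be said that a 20-drop target is a strained reading, since 10 drops three times a day is fully within the prescription. That is fair, and a 10-drop target is easier to defend. It leaves the other error: a 20-drop patient passes on a quarter of the doses. A minimum total exposure would be a legitimate per-protocol rule, but section 8.4 presents its rule as one of compliance.

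Two stronger readings are tempting, and the document supports neither.
- A reader might infer that neither end of the range measures adherence. Each end does equal 50% adherence for patients who stay at that dose; the error concerns patients at other doses.
- A reader might infer that sections 8.4 and 11.4.3 conflict. Excluding below 50% and including at least half are complementary. Section 11.4.3 would differ only if read as half of the dispensed 50 ml bottle (25 ml), which is not the natural reading.

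**Conclusion.** The point holds as a defect in how compliance is defined and recorded. The cut-off has a two-fold range, 10.5 to 21 ml, and at any single volume the adherence required of a 10-drop patient is twice that required of a 20-drop patient.

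The reach is limited. It concerns the secondary per-protocol analysis and compliance as a predictor in section 4.3. The primary analysis in section 11.4.2 includes patients with completed questionnaires whatever their compliance, so it and the sample size are untouched. How many patients would be misclassified cannot be worked out, because the protocol gives no distribution of chosen dose or adherence.

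The figures assume 28 treatment days, doses kept within 10 to 20 drops, the stated drop volume, and an app that records no more than the protocol describes. The correction is worth making because it is cheap and because dose detail not recorded during treatment cannot be recovered later.

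**What to change.** 1. Add two numeric fields to the daily app entry and its paper form: doses taken that day (0 to 3) and drops per dose.
2. Define compliance identically in sections 8.4 and 11.4.3: at least 50% of scheduled doses, each of 10 to 20 drops, with scheduled doses = 3 × planned treatment days (42 of 84 for 28 days). Tying the denominator to planned days matters because visit 3 may fall at 28 ± 14 days in the Study Schedule, or 4 to 6 weeks after visit 2 in section 9.3.2.
3. Use the dose count as the compliance predictor in section 4.3 (viii).
4. Keep bottle weight as an objective check. For 28 days, use below 10.5 ml means fewer than 42 doses at any permitted dose, and use of at least 21 ml means at least 42.
5. For patients already treated, classify by bottle weight alone: below 10.5 ml non-compliant, at least 21 ml compliant, and 10.5 to below 21 ml undetermined. Report the per-protocol result with and without the undetermined group. Do not count a missing app entry as a missed dose; sections 6.1 and 6.2.3 foresee irregular reporting and plan calls to such patients.

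The cost is a few sentences and two fields in an entry patients already make, with no new visit or measurement. The downside is reliance on self-reported dose counts, which bottle weight checks only in part.

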8.5 Data Collection and Follow-up for withdrawn participants

In the event of withdrawal, the data collected up to this point will continue to be used.

8.6 Trial specific preventive measures

Treatment with Amara during the last one month prior to the study is not permitted and leads to the exclusion of the study. No specific preventive measures are necessary.

8.7 Concomitant Interventions (treatments)

Current medications, such as acid suppression or antidepressants, can continue to be taken by the participants during the study without dose increase or decrease. This also includes all self-purchased preparations that are available without a doctor's prescription and complementary-medical preparations. Participants will record the use of additional medication in the CRF. They also have to record if they are being treated by other physicians during the study.

8.8 Study Drug Accountability

Immediately after handing out the study drug a receiving inspection will be carried out using the delivery note and the order form. Information on quantities, batch number, damages and shelf life will be recorded in writing in the corresponding Standard Operating Procedure (SOP) document.

In case a participant has signed the informed consent, at the end of the consultation one 50ml bottle of Amara will be given to the participant to take home. The distribution of the test substance will be signed

by the participant and IP on the SOP document. Drugs with the shortest expiry date will be distributed first. Regular expiration date checks will be carried out.

Patient compliance will be assessed using a smart phone application that will record whether medication was taken and the severity of symptoms at the end of each day. Patient compliance (i.e. actual intake) will be checked by weighing the bottle at the end of the treatment period.

8.9 Return or Destruction of Study Drug

Participants are asked to send back the glass with the remaining liquid. The study team will check compliance (i.e. actual intake) by weighing the bottle at the end of the treatment period and then send the investigational product to the pharmacy (Apotheke Klinik Arlesheim) for destruction. The handover will be documented in writing in a SOP.

9. STUDY ASSESSMENTS

9.1 Study flow chart(s) / table of study procedures and assessments

9.2 Assessments of outcomes

The primary study outcome of dyspeptic symptoms will be assessed by the LDQ three times (screening, baseline, study completion).

Secondary study outcomes will be assessed (i) by other validated questionnaires assessing gastrointestinal and psychological comorbidity as well as (ii) by physiological measurement of gastric motor and sensory function using the NTM Drink Test with ¹³C measurement of gastric emptying (section 5). Additionally, the Lüscher Colour Test will be performed to assess the psychological state and personality profile potentially changing during treatment (section 5.3).

9.2.1 Assessment of primary outcome

See section 5.1.

9.2.2 Assessment of secondary outcomes

See section 5.2.

9.2.3 Assessment of other outcomes of interest

See section 5.3

9.2.4 Assessment of safety outcomes

9.2.4.1 Adverse events

AEs will be recorded, although the Swiss law on clinical research does not require the documentation of AEs for Category A drug trials. Participants will record possible side effects in the app or booklet and are instructed depending on urgency to get in touch with the team of doctors.

Information to be collected about side effects can be seen in chapter 5.4.

9.2.4.2 Laboratory parameters

Urine pregnancy tests will be carried out during the screening visit. In emergency situations laboratory parameters may be assessed if required.

9.2.4.3 Vital signs

No vital signs will be assessed in the context of the study except in emergency situations which may require it.

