ШΤ	Investigator-initiated Trial
KLA	Klinik Arlesheim
LCT	Lüscher Colour Test
LDQ	Leuven Dyspepsia Questionnaire
NTM	Nottingham Test Meal
OTC	Over The Counter
PHQ-12	Patient Health Questionnaire 12-items, depression module
PI	Principal Investigator
RCT	Randomised Controlled Trial
RDQ	Reflux Disease Questionnaire
SAE	Serious Adverse Event
SDV	Source Data Verification
SOP	Standard Operating Procedure
SPC	Summary of product characteristics
SUSAR	Suspected Unexpected Serious Adverse Reaction
TMF	Trial Master File

STUDY SCHEDULE

Study Periods	Screening	Physiological Measurement and Treatment	Physiological Measurement and End
Visit	1	2	3
Time (days)	Ca14-28d	1	28±14d
Medical History and Demographics	x		
Leuven Dyspepsia Questionnaire (LDQ)	x		x
Screening questionnaires	x		
Pregnancy test (urine)	x	(x)	
In-/Exclusion Criteria	x		
Patient Information and Informed Consent	x		
Primary Outcome Measure: LDQ total score	x		x
Secondary Outcome Measure: other GI symptom questionnaires	x	x	x
Lüscher Colour Test	x	x	x
Physiological Measurement (13C BT, HRV)		x	x
Intake of the Study Medication (Amara Drops)		x	x
Compliance with therapy			x
Satisfaction with therapy / Whether a prescription of Amara is wanted			x
Concomitant Medication, Therapy	x	x	x
Serious Adverse Events	x	x	x

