7.1 Eligibility criteria

Participants fulfilling all of the following inclusion criteria are eligible for the study:

- Patients referred by their treating physician to the Center for integrative Gastroenterology at the Clinic Arlesheim
- Age over 18 years and \leq 75 years of age
- Patients with diagnostic criteria of Functional Dyspepsia with Postprandial Distress (Rome IV criteria) with Leuven Dyspepsia Score "at least moderate" severity (≥2/4) on at least two subscales (≥4 total). Normal endoscopy in previous 3 years.
- Signed informed consent
- No change in medical treatment (e.g., proton pump inhibitor, antidepressants) during the last one month or for the duration of the period
- No planned introduction or dose increases of (conventional) anxiolytics or antidepressants during the last one month or for the duration of the period
- Good German knowledge (at least level B2 from Common European Framework of Reference for Languages)

The presence of any one of the following exclusion criteria will lead to exclusion of the participant:

- Acute life-threatening conditions
- Withdrawal of informed consent
- Clinically relevant psychiatric comorbidity (HADS score >11 for anxiety or depression)
- Advanced liver (Child score > 6) or kidney disease (GFR < 60)
- History of major gastrointestinal surgery (appendectomy, hysterectomy, cholecystectomy, hernia repair are not exclusion criteria)
- Allergy to any component of Amara
- Treatment with Amara during the last one month prior to the study
- Pregnancy and lactation

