7.4 Criteria for withdrawal / discontinuation of participants

In emergency situations, where acute symptoms develop or side effects are suspected to be associated with the Amara intake, treatment can be discontinued. The participation can also be terminated by the PI, by the Clinic Arlesheim or by the manufacturer of Amara if there is a suspicion of damage to health caused by the drug or a product defect, respectively. Also, as mentioned before, if there are any signs of patients unwilling to participate in the study it will result in the participant being excluded from the study.

If a participant does no longer fulfil the eligibility criteria at some point of the study, it will lead to the discontinuation of this participant from the study.

Participant recruitment will continue until 60 patients have completed the treatment arm of the study.

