9.3 Procedures at each visit

9.3.1 Screening visit

At the orientation consultation/screening visit the investigator will review the case notes, investigation results (e.g., laboratory tests, gastroscopy) and interview the patient to ensure that inclusion and exclusion criteria are met. In order to comply with the inclusion criteria, pregnancy tests will be performed on all women of childbearing age. At the screening visit, the LDS and HADS questionnaires will be completed at the time of recruitment and used as screening instruments. This data will be collected using an on-line application. After inclusion, further health-related questionnaires will be completed and

the Lüscher Color Test will be performed.

A time is booked 2-4 weeks later for the second study visit. A mobile application will be downloaded onto the personal smart phone device (Symptom Tracker, Gastric Imaging & Analysis GmbH). Paper forms are available if required. During the 2-4 week "run-in" period patients will document their symptoms every day using a mobile application. A reminder will be sent to complete this electronic form every day at 21:00.

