9.3.2 Study visits

On the second visit, patients will complete a combined assessment of gastric motor and sensory function off treatment with the Nottingham Test Meal, with gastric emptying documented by ¹³C-Breath Testing. On completion of the test, the test substance will be provided to the patient with instructions on how and when to take the Amara. An appointment will be made 4-6 weeks after this appointment for the third and final visit. Based on this, the start day for the intervention will also be determined.

During the 4-week intervention, 10-20 drops of Amara will be taken prior to every meal. Patients will document their symptoms every day using a mobile application. Adverse events can also be recorded. Paper forms are available if required. A reminder will be sent to complete this electronic form every day at 21:00.

Shortly before the third study visit participants receive an e-mail with a questionnaire link. All questionnaires will be completed again. If it is noted during the visit that the questionnaires has not been filled in, this can be done in the waiting room or during the visit. The patient will complete a combined assessment of gastric motor and sensory function on Amara treatment with the Nottingham Test Meal, with gastric emptying documented by ¹³C-Breath Testing. On completion of the test, in addition to the PROM, the patient will be asked about their subjective assessment of the intervention, whether ongoing treatment is desired and whether they would recommend the treatment to other patients with functional dyspepsia. Additionally, compliance with study procedures will be assessed (bottle(s) of Amara will be weighed). At the end of the study, patients are reimbursed a lump sum of 50 Swiss francs for expenses (gas, parking fee, train ticket etc.). More can be provided if an invoice supported by receipts is sent to the principal investigator.

In a subset of 20 consecutive patients, gastric electrical activity will be measured before, during and after ingestion of the Nottingham Test Meal on the second and third study visit using the non-invasive Gastric Alimetry System (high-resolution gastric mapping / electro-gastrography). Concurrent heart rate monitoring will provide an assessment of cardiovagal tone / autonomic nervous function.

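### First dose can rest on a pregnancy test 14 to 28 days old, and the protocol shown sets no active outcome collection for a pregnancy exposed to Amara

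*Protocol*

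**What the plan says.** Section 7.1 lists "Pregnancy and lactation" among the exclusions. The text on testing is spread over several places:

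- **9.2.4.2:** "Urine pregnancy tests will be carried out during the screening visit". No later routine test is named.
- **9.3.1 (screening visit):** "pregnancy tests will be performed on all women of childbearing age". Section 7.2 likewise treats the test as part of screening.
- **Study schedule:** the row "Pregnancy test (urine)" has an x at visit 1, an x in brackets at visit 2 and nothing at visit 3.
- **9.3.1, timing:** "A time is booked 2-4 weeks later for the second study visit".
- **9.3.2 (visit 2):** "On completion of the test, the test substance will be provided to the patient". The test meant here is the breath test.
- **8.8:** ties hand-out of the bottle to signed consent and the end of the consultation. It also does not mention a pregnancy result.
- **7.4:** "If a participant does no longer fulfil the eligibility criteria at some point of the study, it will lead to the discontinuation" of that participant.

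On a pregnancy that occurs in the study, 10.1.2 has a paragraph on reporting and handling whose only content is that pregnant participants are excluded. Its list of what goes to the manufacturer does not name pregnancy. Section 9.2.5 says that participants withdrawn for exclusion criteria other than SAEs need no follow-up, and it points to chapter 10 for the rest.

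**The concern.** The exclusion protects a woman only if pregnancy is ruled out close to the time she starts the drug. The run-in separates the screening test from dosing by weeks. A site that works from the body text could start treatment without testing again, so a pregnancy that begins or becomes detectable in the run-in could be missed. Section 7.4 would remove a participant known to be pregnant, but the body text requires no test at visit 2 that would reveal it.

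The second part concerns what happens after exposure. If a participant is found to be pregnant while taking Amara, the protocol withdraws her, and on its own wording she then needs no follow-up. The outcome would be learned only if she volunteered it. At stake are her safety and the safety information on the product. No efficacy estimate depends on it.

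**Working it through.** The plan gives no figure of its own here. The check is date arithmetic on the stated intervals and a side-by-side reading of the safety sections.

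**Age of the test at first dose**

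1. Screening to visit 2 is 2 to 4 weeks (9.3.1), and the schedule gives about 14 to 28 days: 2 × 7 = 14 and 4 × 7 = 28.
2. The schedule marks intake of the study drug at visit 2. With the required test at screening and the first dose at visit 2, the test is **14 to 28 days** old.
3. With a required test at visit 2 and the first dose on that day, the interval is 0 days, a reduction of 14 to 28 days.
4. Sections 8.8 and 9.3.2 differ on hand-out. If 8.8 means hand-out at the first consultation, the interval from test to hand-out is shorter, but the interval to a first dose at visit 2 is still 14 to 28 days. The firm statement is therefore about first dose, not about dispensing.
5. Section 9.3.2 also lets the start day depend on when visit 3 is booked. A later start would lengthen the interval, but no rule for the start day is stated, so no upper figure is given here.

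**Is a negative result a condition anywhere?**

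| Place | Test named? | Condition for hand-out or first dose? |
|---|---|---|
| 7.2, 9.2.4.2, 9.3.1 | Yes, at screening | No condition at visit 2 |
| Study schedule, visit 2 | Yes, in brackets | Not stated |
| 9.3.2 | No | No; follows the breath test |
| 8.8 | No | No; follows consent |

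**Does the outcome of an exposed pregnancy get collected?**

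1. 10.1.2: exclusion only.
2. 9.2.5: pregnancy is an exclusion criterion and is not in itself an SAE, so the waiver of follow-up covers it.
3. Chapter 10, to which 9.2.5 points: 10.1.3 deals with SAEs still ongoing.
4. 10.1.1 classes a congenital anomaly as an SAE, but 10.1 ends collection at the last protocol procedure. Visit 3 is booked 4 to 6 weeks after visit 2, so from visit 1 it falls at most 28 + 42 = **70 days** later. A pregnancy that starts in the run-in or on treatment would reach birth well after that.
5. 5.4 and 4.4 allow or encourage later reports, but the participant has to make them.

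**The case against.** The strongest reply is that the schedule is part of the protocol and already lists a urine test at visit 2. The brackets may mean a test before dosing in women of childbearing potential. The section headed "Study flow chart(s) / table of study procedures and assessments" has no content in the text available, so a key may simply have been lost. This stands: the absence of a key is not held against the plan. Nor can a reader infer that there is no test after screening. Sections 9.2.4.2 and 9.3.1 place the test at screening without ruling out a later one. What remains is that the procedural text at visit 2 neither requires the test nor makes its result a condition.

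A second reply is that reporting detail lies elsewhere. Section 10.1 refers to the sponsor's SOPs, and 10.1.2 refers to obligations under the manufacturer contract. Neither is shown. This also stands in part. A reader might infer that exposed pregnancies will go unreported, but the document does not support that. It shows only that the protocol text does not provide for it, and that 9.2.5 points the other way.

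Third, there are partial safeguards: 7.4 withdraws a participant known to be pregnant, a congenital anomaly counts as an SAE, late reports are accepted, and 9.2.5 does not forbid follow-up. The product is marketed and treatment lasts 28 days. These points keep the matter minor, but none of them provides a test before dosing or a planned contact afterwards.

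**Conclusion.** The point holds as a minor one, on participant safety only. As the body text is written, a first dose at visit 2 can rest on a pregnancy test 14 to 28 days old. No section makes a negative result at visit 2 a condition for hand-out or dosing. For a pregnancy exposed to Amara, the protocol specifies exclusion, waives follow-up and plans no contact to learn the outcome.

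The interval assumes that dosing starts at visit 2, as the schedule marks it, and that the bracketed test is not treated as compulsory. It should not be read as a fixed interval to dispensing, because 8.8 and 9.3.2 disagree on when the bottle is handed out. The number of women affected cannot be derived from the document. The sample size and the primary analysis are unaffected.

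**What to change.** Changes in six places:

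- **Study schedule:** replace the bracketed x at visit 2 with a plain x, for women of childbearing potential.
- **9.2.4.2 and 9.3.2:** state that a negative urine test at visit 2 is required before Amara is handed out and the first dose is taken.
- **8.8:** state the same condition, and align the text with 9.3.2 so that hand-out is at visit 2.
- **9.2.5:** except pregnancies exposed to study drug from the sentence that waives follow-up.
- **10.1.2:** require that such a pregnancy is recorded, notified to the manufacturer and followed to its outcome after the participant is withdrawn.

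The cost is one urine test per woman of childbearing potential, which the schedule already lists, and one later contact for a rare event. If the SOPs or the contract already cover exposed pregnancies, 10.1.2 can refer to them, but the waiver in 9.2.5 still needs the exception.
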